Patient-centered e-health has failed to achieve its promise despite considerable consumer interest in technology and research supporting its potential. E-health adoption rates in healthcare are poor, with specialty substance use disorder (SUD) treatment having the lowest technology adoption rate of any sector.¹ Implementation science can address this emerging gap in the e-health field by augmenting existing models, that explain organizational and individual ehealth behaviors retrospectively, with prospective models that can guide implementation. The organizational planning discipline, with its decades of research, could provide a cross-disciplinary “jump start” to developing an e-health implementation model for health organizations.^{2,3} Henry Mintzberg, a respected pioneer in this field, describes 2 beneficial approaches to planning: the *deliberate approach*, which is grounded in pre-implementation planning, and the *emergent approach* that is grounded in adapting to the environment as the plan is implemented.⁴ The proposed e-health implementation model, called the Network for the Improvement of Addiction Treatment–Technology Implementation (*NIATx-TI*) *Framework*, incorporates both approaches.

NIATx-TI was piloted in the Iowa Rural Health Information Technology Initiative (IRHIT) with 14 of Iowa’s 105 SUD treatment sites and resulted in a 2-fold increase in patients receiving distance treatment. The framework’s *deliberate* component includes using an organizational technology assessment⁵ and patient simulation.⁶ These tools identify and address assets and barriers to incorporate into the technology’s implementation protocol. The framework’s *emergent* component includes using a project team to uncover and prioritize implementation barriers as they arise, develop changes to address identified barriers, and monitor selected adoption measures, while receiving monthly coaching.

This project, based in Iowa, will compare a control condition (using a typical product training approach to software implementation that includes user tutorials and instruction on administrative and clinical protocols, followed by access to on-line support) to the typical product training combined with NIATx-TI. While e-health spans many modalities and health disciplines, this project will focus on the implementing Addiction Comprehensive Health Enhancement Support System (A-CHESS), an evidence-based SUD treatment recovery app developed by our Center for a disease that affects 21.5 million and kills 136,000 Americans annually: substance use disorder.⁷ A mobile app was selected, as opposed to another e-health technology, because of the near ubiquitous daily use of mobile technology and because mobile e-health adoption requires supportive participation of both health centers and patients.

In response to the COVID-19 pandemic, we have added a study component focused on describing how patients are responding to receiving remote treatment (e.g., telehealth). We will also seek to understand how using A-CHESS mitigates COVID-19 associated anxiety and loneliness among those with substance use disorders.

1. BACKGROUND AND SIGNIFICANCE

This project addresses an issue of substantial public health significance: enhancing the uptake of the growing list of patient-centered evidence-based addiction treatment e-health technologies.

Substance Use Disorders (SUDs) Impact on Society and Health. Every day on average, 96 Americans die due to opioid overdoses and another 6 die due to alcohol poisoning, making SUDs the third-leading cause of preventable death in the United States.⁸ Many injuries and

diseases (e.g., cancer, diabetes, cardiovascular problems, cirrhosis, and HIV/AIDS) are caused or exacerbated by alcohol abuse.⁹ Despite the health and societal consequences of SUDs, just 9.2% of those who need treatment receive it⁷ and, for those treated, 75% fail to achieve longterm sobriety.¹⁰ **The gap between the need for and the effectiveness of SUD treatment services calls for implementing fundamentally different treatment modalities to improve SUD.**

Patient-centered Mobile E-health: A Potential Answer? Patient-centered mobile e-health technologies offer innovative ways to improve treatment and recovery supports for SUDs.¹¹ Seventy-seven percent of the adult population in United States currently have a smartphone,¹² as do 74% of adults accessing Iowa SUD treatment clinics. By 2020, over 95% of the US population is expected to have smartphone access.¹² Meta-analyses of mobile behavioral ehealth interventions have found superior treatment outcomes when compared to treatment as usual.^{13,14} The combination of consumer interest, research evidence, and the number of research dollars being dedicated to evaluating these technologies will continue to place positive pressure on the use of e-health. **Despite the promise of e-health, its potential benefits are far from being realized.**¹⁵⁻¹⁷ A prominent example of this is in SUD care. Despite the availability of evidence-based e-health tools such as the Drinker's Check-up,^{18,19} Therapeutic Education System (TES),²⁰ CBT4CBT,²¹ and A-CHESS, none of these technologies are used by >1% of SUD treatment providers.²² **This proposal tests the premise that an evidence-based technology implementation framework can reduce the gap between patient-centered ehealth evidence and practice.**

Technology Adoption Models: Strengths and Needs. Extensive research supports building models to speed diffusion and sustainability of technology adoption.²³ Technology adoption research began with models, grounded in behavioral change,²⁴ explaining why individual users abandon traditional practices in favor of new technologies.²⁵ Over time, these individual-focused models have had to expand because of the necessary role organizational practices and climate play in individual decisions to adopt and continue to use a technology.^{26,27} Explanatory models emerged based on 2 prominent frameworks: the diffusion of innovation and the technology, organization, and environment framework.²⁴ These frameworks include the key organizational factors of management support, clinician satisfaction, clinical workflow, and financial resources for technology purchase, implementation, and use.^{28,29} Financial resources such as start-up grants and reimbursement supporting technology use are important factors in technology adoption. However, reviews by Brooks²⁸ and Jeyaraj²⁹ demonstrate that reimbursement cannot be the only issue considered. Two health technology implementation projects conducted by our Center in 7 different states during 2012–2015 confirmed that patient, clinician, and organizational as well as financial barriers can limit technology adoption. In seeking approaches to address these multi-faceted barriers, we were surprised to find that most models described the barriers,^{30,31} but not how to address them. **In seeking technology implementation models, we realized the organizational planning field could provide the frameworks needed to address the competencies and processes that remained unexplored in previous technology implementation research.**

Planning Model Theory as a Conceptual Foundation for Network for the Improvement of Addiction Treatment (NIATx)- Technology Implementation (TI): Two important evolutions have created a planning field that has remained relatively stable in theory and approach for the past 2 decades.³² The first was Porter's (1979)³³ 5 competitive forces framework, which created a foundation for deliberate planning. This "look before you leap" planning approach relies on a centralized planning function and development of "the plan." Concerns with this methodology led Mintzberg and Waters (1985)⁴ to assert that Porter's *deliberate* (sometimes called

prescriptive) planning for organizational strategy and change was necessary, but not sufficient. Simply too much occurred once a plan was hatched. Their *emergent* (sometimes called *descriptive*) *planning* approach used data that emerged from the implementation process to improve the plan. This moved planning from a purely centralized (top-down) process to include a more emergent (staff engaged) approach.³⁴⁻³⁶ Using these concepts, our Center, The Center for Health Enhancement Systems Studies (CHESS), searched through our field experiences³⁷⁻⁴⁰ and the literature, for pre-implementation (*deliberate*) as well a post-implementation (*emergent*) strategies capable of quickly adjusting to environmental feedback to construct the NIATx-TI ehealth implementation framework.

Mobile Technology as a Focus was selected because of its pervasive use, the evidence base for the CHESS platform that supports A-CHESS, and our familiarity with A-CHESS. A-CHESS is based on the CHESS platform, which has been studied in 16 randomized control trials (RCTs) over 16 years, using several technology media.⁴¹⁻⁴³ These RCTs, each involved hundreds of people, found that the CHESS platform improved key dimensions of quality of life,⁴¹

⁴⁴ health behavior adherence (e.g., smoking cessation and risky drinking),⁴⁵⁻⁴⁷ and outcomes (e.g., lung cancer death rates and sobriety). A-CHESS is consistent with respected health behavior change models such as self-determination theory (SDT)⁴⁸ and Marlatt's Cognitive Behavior model⁴⁹ of relapse prevention. In a randomized trial (N=349), patients using A-CHESS, compared to those in the control group, reported 51% fewer risky drinking days in the prior 30 days at the 4-, 8-, and 12-month follow-ups (mean of 1.39 days in A-CHESS vs. 2.75 days per month in TAU, $p = .003$). Rates of alcohol abstinence were significantly higher among A-CHESS patients at 8 months (78% vs. 67%) and 12 months (79% vs. 66%).⁵⁰ The A-CHESS app includes educational materials, discussion groups, links to SUD resources and weekly self-monitoring for patients. The CHESS platform has also been an effective method for clinicians to interact with their patients.⁵¹ A-CHESS provides a report for clinicians that delivers to the clinician team information about worrisome changes in symptoms collected from the patient during self-monitoring of risk-related items (i.e., sleeping problems, depression, urge, risky situation and relationship troubles).⁵² A-CHESS contacts the clinical team by email, phone, or fax (according to clinician preference) whenever a threshold symptom is reported. The alert was intended to quickly bring clinician attention to emerging symptoms.

Technology like A-CHESS is a potential game changer: it can provide recovery supports 24 hours a day, 7 days a week and can be customized to individual needs. **This research will test a technology adoption framework to increase use of the A-CHESS smartphone app.** A supplemental study will help understand how A-CHESS may help patients manage increased levels of anxiety and loneliness during the COVID-19 pandemic.

2. STUDY OBJECTIVES

The specific aim of this study is to compare the effectiveness of NIATx-TI (Arm 2) and Product Training (Arm1) in implementing an evidence-based innovation (A-CHESS). Impact will be measured using the RE-AIM framework:⁵³

- Reach or Participation (Primary Outcome): a) percent and representativeness, based on age, gender, and ethnicity by organizational site, and b) A-CHESS use per each counselor, by days of use;
- Effectiveness: retention rates of eligible patients overall

- Adoption: percent and representativeness, based on age, gender, race, ethnicity, and education level of counselors referring and not referring patients to A-CHESS;
- Implementation: a) organizational readiness for, and b) fidelity of A-CHESS implementation; and c) qualitative and d) cost effectiveness analyses to develop a better understanding of the implementation processes for delivering NIATx-TI compared to product training alone; and
- Maintenance: A-CHESS use (e.g., A-CHESS downloads and days of A-CHESS use) during the post-test phase.

The specific aims of the COVID-19 supplemental study are 1) to understand whether using A-CHESS may help patients manage anxiety and loneliness associated with social isolation, physical distancing, and other changes to daily life during the COVID-19 pandemic, and 2) to understand how patients have adapted to changes in treatment modality during the COVID-19 pandemic. Impact will be measured by offering all patients who have ever signed up for an A-CHESS account the chance to complete an online survey (administered through REDCap) as well as the opportunity for a qualitative interview with a member of our research team using a standardized interview guide.

Study Coordination

The UW-Madison Center for Health Enhancement Systems Studies (CHESS) is the coordinating site for this study. The UW study coordinator will oversee all recruitment activities which includes:

- developing organizational site-specific recruitment and data collection processes that meet study objectives;
- training staff on protocol procedures prior to start of recruitment and continuous monitoring to assure compliance with the protocol and human subjects regulation;
- communicating with clinic site staff as needed via conference calls to monitor progress, inform of protocol changes/distribute new version of protocol, and address unanticipated issues or challenges;
- and manage all study data.

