9. STATISTICAL CONSIDERATIONS

Sample Size, Power & Data Analysis Plan: We will fit a mixed-effects model with the appropriate link function (e.g., linear, log) to the monthly results for the performance measures, % of eligible A-CHESS users and frequency of A-CHESS use, for each of the participating organizational sites, clustered by organization, and estimate the NIATx-TI framework and

product training effects. A mixed-effect model offers 2 advantages over conventional regression models: 1) The mean outcomes for a given treatment organization are expected to be correlated from month to month. A mixed-effect model allows for auto-correlated error terms. 2) Many unobservable treatment organizational site characteristics are likely to influence the key measures. Random effects at the treatment organization site level can be employed within the mixed-effect model to capture the correlation introduced by such characteristics. Proper reflection of auto-correlation and random effects allows for more reliable estimates of the fixed effects, starting at baseline, then again during the 18-month test and post-test periods. The power of the study design is determined by the anticipated standardized effect size based on effects experienced in the IRHIT project. The standardized effect size is calculated following Cohen's definition of mean effect size divided by effect size standard error.⁶⁵ The higher the standardized effect size, the more powerful the study design. Historically, cluster-randomized trials portray the standardized effect sizes of 0.2, 0.5 and 0.8 as small, medium, and large respectively. The IRHIT pilot data found that NIATx-TI increased client technology use rates by 12.4% (increase of intervention success), which can be transformed into Cohen's $d = 0.352$.⁶⁶ Intraclass correlation (ICC) among sites affects the power of cluster-randomized trials.⁶⁷ An estimate of ICC is around 0.10.⁵⁰ With a total of 8 organizations, with 20 organizational sites in each arm, where each site has an average 62 eligible patients, the study will achieve a power of .90 with a type I error rate of 0.05.

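### Reach, the primary outcome, has two modelled measures but one 0.05/.90 statement, and the plan does not say how the 0.05 applies across them

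*Combined protocol and SAP*

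**What the plan says.** Section 2 (Study Objectives) attaches the primary label to one RE-AIM dimension, Reach, and splits it in two. The first part is "Reach or Participation (Primary Outcome): a) percent and representativeness", with the latter judged on demographic traits within each site. The second part is "b) A-CHESS use per each counselor, by days of use". Table 1 (Section 5) and Section 7 also list two Reach measures: the share of patients who download the app, and use in days.

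Section 9 fits mixed-effects models to the "monthly results for the performance measures, % of eligible A-CHESS users and frequency of A-CHESS use". It estimates "fixed effects, starting at baseline, then again during the 18-month test and post-test periods". The sample-size text rests on one pilot effect, a 12.4% increase in a technology use rate (d = 0.352), and concludes that "the study will achieve a power of .90 with a type I error rate of 0.05". No effect size is given for days of use.

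Post-test use is listed in Section 2 under a different dimension: "Maintenance: A-CHESS use (e.g., A-CHESS downloads and days of A-CHESS use) during the post-test phase". That dimension is not labelled primary.

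Neither Section 2 nor Section 9 gives an order of testing, a division of the 0.05, a rule that both measures must succeed, or any other handling of multiplicity.

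**The concern.** A single error rate and a single power describe a trial with one deciding test. Here the primary outcome has two measures, and each yields its own comparison of arms. Without a decision rule, the team could choose after seeing the results which measure stands for Reach. A reader of the final report could not tell what false-positive risk lies behind a positive primary result, or what chance the trial had of producing one.

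The second measure is also not consistently defined. Days of use are per counselor in Section 2, modelled by site in Section 9, and collected by app user for 12 months from first use in Section 5 (Use data). The last version exists only for patients who download the app.

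**Working it through.** **Inputs (Section 9).** d = 0.352; ICC 0.10; 20 sites per arm; 62 eligible patients per site on average; type I error 0.05; power .90. Assumed: two-sided testing (not stated) and a range for the correlation between the two test statistics (not given).

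**Step 1: reproduce the plan's figure.**
- Design effect = 1 + (62 − 1) × 0.10 = 7.1.
- Effective number per arm = 20 × 62 / 7.1 = 174.6.
- Power = Φ(0.352 × √(174.6/2) − 1.96) = Φ(3.289 − 1.96) = Φ(1.329) = 0.908. A t reference with 38 degrees of freedom gives 0.893.
- One-sided 0.05 would give 0.950, so the two-sided reading fits.

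The stated .90 is therefore the power of one comparison at two-sided 0.05. This follows the plan's clustering by site; whether that is the right cluster for a design that randomizes organizations is a separate question.

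**Step 2: either measure can win.** Familywise error = 1 − P(|Z1| < 1.96 and |Z2| < 1.96), with both null hypotheses true.

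| Correlation | Familywise error |
|---|---|
| 0 | 1 − 0.95² = 0.0975 |
| 0.5 | 0.0907 |
| 0.8 | 0.0781 |

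**Step 3: both measures must win.**
- Error: at most 0.05. With no effect on either measure, the chance that both tests are significant is 0.0025 at correlation 0 and 0.0219 at 0.8. It can approach 0.05 only when one measure has a real and almost certainly detected effect.
- Power: no higher than that of the weaker test. If each test had .90, joint power would lie between 0.90 + 0.90 − 1 = 0.80 and 0.90, and would be 0.90 × 0.90 = 0.81 under independence. Equal power is an assumption, since no effect size is given for days of use. If days of use has less power, the ceiling is lower.

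**Step 4: divide the 0.05 equally.** At 0.025 per measure, the Step 1 power becomes 0.853 (t: 0.826).

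Only a single deciding measure, or a sequence that starts with the powered one, leaves both stated figures intact.

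**The case against.** The strongest reply is that the plan never claims a familywise rate. Its 0.05 is an input to a power calculation, and as such it is consistent with the .90. Section 2 also joins the two parts of Reach with the word and; if both were required, there would be no inflation. This stands in part. A reader might infer that the design fails to have the error rate it states, or that the false-positive risk is nearly doubled. The documents do not support either as a flat claim, because inflation needs an either-one-wins rule that they do not state. But the conjunction joins items in a list and is not a decision rule. If it were read as one, the .90 would no longer describe the power of the primary claim.

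A reader might also count four primary tests, two measures in two periods, and arrive at 1 − 0.95⁴ = 18.5%. That does not hold. Section 2 puts post-test use under Maintenance, and estimating an effect in a period does not make it primary. The figure also assumes independence, whereas Section 9 expects correlation from month to month.

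Finally, the pilot effect is a technology use rate, and the opening summary describes the pilot result as patients receiving distance treatment. The documents do not identify it as app downloads. That is correct: a rate is closer to the download percentage than to days of use, but the link is an inference.

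**Conclusion.** The point holds in a limited form: the plan does not say how 0.05 applies across the two Reach measures, so the familywise error and the power of the primary claim are undefined. If either measure can win, the error is about 7.8% to 9.75% for correlations from 0.8 to 0. If both must win, the error is at most 5%, and .90 is not established (about 0.81 under equal power and independence). These figures assume two-sided tests and a correlation that the documents do not give. The supported count is two primary measures; post-test contrasts are not among them. This is a gap in specification that is cheap to close, and it does not show that the design is invalid.

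**What to change.** In Sections 2 and 9:
- Name the percentage of eligible patients who download A-CHESS over the 18-month intervention period as the single primary measure, and state which arm contrast from the monthly model carries the test. The reason for this choice is that the effect behind the power figure is a use rate and is closest to this measure.
- Test days of use second, at two-sided 0.05, only if the first test is significant. Before that, reconcile its unit across Section 2 (counselor), Section 9 (site) and Section 5 (app user).
- Report representativeness, the post-test (Maintenance) contrasts and the analyses after each NIATx-TI stage mentioned in Section 9 as estimates with intervals.

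The sequence holds the error over the two tests at 0.05 and leaves the planned power of the first test unchanged. Requiring both measures, or testing each at 0.025, would also settle the error rate, at the cost in power shown above.

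The change is to wording, but it should be made by dated amendment that states whether comparative data had been seen: Section 3 reports 520 patient accounts already created, and Section 5 has the evaluation team monitoring use. The downside is that a benefit in days of use alone can no longer make the trial positive.

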3. SELECTION OF SUBJECTS

This study will engage SUD organizations, counseling and peer recovery support specialist staff at those organizations, and patients of those organizations.

Organizations: Sixteen SUD organizations in Iowa, with a total of forty sites, have agreed to participate in the project.

Counselors: The site coordinator will invite all outpatient counselors serving adult patients employed by the 16 SUD organizations to be part of the study as part of their role in the participating organizations. Any counselor may formally decline to participate during the training or any time thereafter.

Peer Recovery Support Specialists: Peer Recovery Support Specialists associated with the organization will be invited to be part of the study. Any Peer Recovery Support Specialists may formally decline to participate during training or any time thereafter.

Patients: We will aim to enroll 1,800 outpatients from the 16 enrolled organizations. Each organization is expected to have about 516 A-CHESS-eligible patients on average. We estimate that we will recruit a conservative 30% (or approximately 43 per organizational site) for a total n=1,800 patients in the study. We will recruit patients for the 18-month intervention period plus 6 months into the maintenance period. Patients are eligible for the study if they:

- Are 18+ years old
- Understand English
- Have a SUD diagnosis
- Have access to a smartphone

All patients will be offered the opportunity to complete a survey through REDCap. To date, n=520 patients have created an A-CHESS account. We will also conduct in-depth interviews with 40 patients who have created an A-CHESS account.

